Detected and statistically characterized lesion targets. Lesions targets were screened for false-positives and then ranked according to PEAK-SUL. The lesion with the hottest PEAK-SUL measurement was designated as the primary lesion.

3.3.1 Preliminary Clinicopathologic Comparison of Endo-HDR with Other Modalities

An initial 9 patients have been enrolled in our prospective Endo-HDR pilot study at Johns Hopkins University (ClinicalTrials.gov Identifier: NCT01226979). This is the first prospective study evaluating Endo-HDR in the U.S. All 8 evaluable patients had tumors <12 cm from the anal verge and no clinical/radiographic suspicious lymphadenopathy outside of the mesorectum (T2-T3, N0-N1). All patients had NCI CTCAE toxicity assessments, MRI, PET/CT, and CEA pre/post-Endo-HDR. RECIST/PERCIST criteria were used to assess response. Surgical specimens were reviewed by a single pathologist. All patients were margin negative and 8 had sphincter preserving surgery (one patient chose to have APR due to poor function prior to treatment). Three of 9 patients (33%) had a pCR of their primary tumors. Toxicity assessments showed only 1 patient with temporary grade 3 proctitis following Endo-HDR. All other toxicities were grade 2 or less, consisting of proctitis and pain managed conservatively.

We have compared surgical specimens of patients treated with endorectal versus chemoradiation with IMRT or 3-dimensional conformal therapy (49). Patients treated with endorectal brachytherapy showed greater treatment ulceration effect on the epithelium, greater hypertrophy of the submucosal rather than adventitial blood vessels and fewer serosal adhesions compared to external beam radiation techniques. See figures below.

[figure not shown]

Figure 3. Representative H&E stained histopathologic sections at 4X magnification from patients who exhibited a complete pathologic response to Endo-HDR (a-e) and conventional external beam radiation (f-j). All images are taken from the region of the rectal wall where the tumor was located prior to neoadjuvant therapy. All insets are shown at 20X magnification. First Row – At the mucosa, extensive ulceration (solid arrows) is apparent after Endo-HDR (a), while the mucosa remains intact (solid arrows) after conventional CRT (f). Hyalinization of the lamina propria (asterisks) is also evident after Endo-HDR (a). Second Row – In the submucosa, marked hypertrophy and sclerosis of vessel walls can be seen following Endo-HDR (b), while only slight hypertrophy of vessel walls is seen after conventional CRT (g). Third Row – Within the muscularis propria, the more superficial interna layer can be seen to exhibit degeneration and atrophy after Endo-HDR while the externa layer remains largely intact (c); in a contrary fashion, following conventional CRT, it is the externa layer that exhibits more prominent degeneration compared to the interna (h). Fourth Row – At the level of the subserosa, vessel walls appear normal in patients treated with Endo-HDR (d), but distinctly hypertrophied in patients treated with conventional CRT (i). Fifth Row - The serosa demonstrates few adhesions (asterisk) after treatment with Endo-HDR (e), in contrast to the extensive adhesions (asterisks) present after treatment with conventional CRT (j).

We propose comparing Endo-HDR versus standard NCRT (IMRT) for stage II/III low rectal cancer (<14 cm from the anal verge). We have focused on patients with distal rectal carcinomas and include patients likely to undergo an APR as they are at highest risk for local failure after TME and most would be excluded in the current national PROSPECT trial. We have also incorporated staging FDG-PET/CT and MRI to exclude any patients with radiographic evidence of pathologic inguinal or iliac lymphadenopathy (defined as >1.5 cm, necrotic on MRI as detailed in the MERCURY study, or suspicious on PET/CT) (29).

4. OBJECTIVES

4.1 Primary Objective

Determine whether Endo-HDR improves pathologic complete response rates when compared to IMRT and capecitabine.

4.2 Secondary Objectives

- Test whether clinical response based on functional imaging (PET, MRI) pre/post radiation (Endo-HDR vs. CRT) predicts for pathologic complete response.
- Utilize preoperative imaging response rates and clinical exam to determine whether Endo-HDR results in improved sphincter preservation rates when compared to CRT.
- Determine whether tumor (VEGF/EGFR status) and blood predict for pathologic response following neoadjuvant Endo-HDR vs. CRT.
- Compare acute and long-term toxicity as well as quality of life for both Endo-HDR and CRT.
- Compare locoregional control, distant metastasis and overall survival for both Endo-HDR and CRT.

5. PARTICIPANT SELECTION

5.1 Inclusion Criteria

- 5.1.1 Histologically confirmed adenocarcinoma of the rectum
- 5.1.2 T2N1-2 or T3N0-2b tumors at \leq 14 cm from the A-V margin (below the peritoneal reflection) or the rectosigmoid junction.
- 5.1.3 Tumors with a lumen sufficient to allow the positioning of the rectal applicator (standard probe/scope) confirmed by the treating physician.
- 5.1.4 Tumors of less than 4 cm thickness from the rectal mucosa documented at the time of staging images
- 5.1.5 Patients should be suitable candidates for surgery and chemotherapy
- 5.1.6 ECOG/WHO performance status 0-1
- 5.1.7 Patients must be 18 years or older
- 5.1.8 No previous history of pelvic radiation
- 5.1.9 Patients must have acceptable organ and marrow function as defined below:
 - Absolute Neutrophil Count $\geq 1.5 \times 10^9/L$
 - Platelets $\geq 100 \times 10^9/L$.
 - Serum creatinine $\leq 1.5 \times ULN$
 - Bilirubin $\leq 1.5 \times ULN$
 - ALT or AST $\leq 2.5 \times ULN$
- 5.1.10 Non pregnant, non-breast feeding females under active contraception
- 5.1.11 Ability to understand and willingness to sign a written informed consent document.

5.2 Exclusion Criteria

- 5.2.1 Evidence of signet ring involvement on histology
- 5.2.2 Evidence of necrotic or > 1.5 cm in diameter pelvic (iliac/inguinal) nodes
- 5.2.3 Evidence of distant metastatic disease
- 5.2.4 Evidence of sphincter invasion on MRI
- 5.2.5 Prior history of radiation to the pelvis

- 5.2.6 Prior malignancy except for adequately treated basal cell or squamous cell skin cancer, cervical carcinoma in situ, DCIS, or other cancer from which the patient has been disease free for at least 3 years
- 5.2.7 Presence of multiple small bowel loops trapped within the immediate tumor bed (post hysterectomy or prostatectomy).
- 5.2.8 Use of any investigational agent within the 4 weeks preceding enrollment
- 5.2.9 Previous exposure to chemotherapy for rectal cancer
- 5.2.10 Uncontrolled intercurrent illness including but not limited to, ongoing or active infections (or infections requiring systemic treatment), symptomatic congestive heart failure, unstable angina pectoris, cardiac arrhythmia, or psychiatric illness/social situations that would limit compliance with study requirements
- 5.2.11 Pregnant and breastfeeding women are excluded, as well as women of child-bearing potential who are unwilling or unable to use an acceptable method of birth control (hormonal or barrier method of birth control; abstinence) to avoid pregnancy for the duration of the study. Should a woman become pregnant or suspect she is pregnant while participating in this study she should inform her treating physician immediately.
- 5.2.12 Women who are not post-menopausal and have a positive urine or serum pregnancy test or refuse to take a pregnancy test.
- 5.2.13 Contraindication for safe MRI, implants, or other conditions that interfere with imaging required for the study (e.g., pacemaker or non-MRI compatible hip prostheses). Note: Subjects with bilateral hip implants are not eligible for the study. Subjects with a unilateral hip implant may be eligible assuming the implant is MRI compatible and does not present artifact on MRI in the areas of interest.
- 5.2.14 Subject is pacemaker dependent.

5.3 Inclusion of Women and Minorities

Both men and women of all races and ethnic groups are eligible for this trial.

6. REGISTRATION PROCEDURES AND RANDOMIZATION

6.1 Informed Consent

All subjects considered from enrollment in the study must complete an IRB approved informed consent prior to any study-specific procedures being performed (Section 13.2).

6.2 Screening/Baseline Assessments and Procedures

The following procedures and assessments will be performed within 6 weeks prior to the initiation of radiation therapy.

- Demographic information
- Medical history and physical examination
- Performance status
- Concomitant medications
- Fiducial marker placement (within 3 weeks of start)
- Research biopsies of tumor and adjacent normal tissue and blood samples (optional)
- FDG-PET/CT
- Pelvic MRI
- CBC w/ diff, CMP, CEA, and testosterone for male participants
- Quality of life assessments
- Assessment of baseline symptoms
- Pregnancy test for women of child-bearing potential

6.3 Fiducial Placement

Endoscopic evaluation will be performed by the surgical team to assess the tumor, ensure adequate lumen for probe placement, and to mark the tumor with MRI compatible gold fiducials (markers) for guidance during **Endo-HDR and CRT** treatment planning. Fiducials should be placed above and below the tumor and the **tumor margins should also be marked with tattoo**. The recommended fiducials to be used are Visicoil™ (0.75mm x 1cm) image markers. When possible, dye should be placed during EUS in the mucosa to demarcate the superior, inferior, and lateral aspects of the tumor.

At the time of endoscopic assessment, tissue biopsies of the tumor may be obtained for correlative studies. After completion of clinical and radiological evaluations under direct rectoscopy, radio-opaque markers are placed to identify the proximal and distal margins of the tumor for subsequent positioning quality control of simulation and treatment applications.

6.4 Registration Procedures

Eligible patients will be entered on study centrally at the Johns Hopkins Hospital by the Study Coordinator.

To register a patient, the following documents should be completed by the research nurse or data manager and sent to the Study Coordinator.

- Source documentation verifying eligibility
- Eligibility checklist
- Signed patient consent form

If the patient is deemed eligible for the study, the Study Coordinator will register the patient and assign a study number.

6.5 Randomization

Eligible subjects will be randomly assigned in a 2:1 ratio to receive either endorectal brachytherapy or IMRT using the method of randomly permuted blocks in strata defined by study site. The patient may be enrolled and randomized before the endoscopic ultrasound and fiducial placement if all eleigibility requirements are met. A master list of randomization assignments will be made by the protocol statistician, and will be delivered to the lead site by email or facsimile report.

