14.2 Sample Size/Accrual Rate

14.2.1 Sample Size and Power

We will screen a total of 165 patients for the trial. Based on our phase II single arm endorectal brachytherapy study, we expect approximately 20% of candidates will drop out because of unexpected findings on PET/CT (i.e. metastases) or MRI (i.e. iliac/inguinal lymph nodes). Therefore, we expect to randomize 138 patients in 2:1 ratio into two treatment arms (92 in the Endo-HDR arm and 46 in the control arm). Using a one-sided Fisher's exact test at significance level 0.1, we will have 80% power to detect a 17% increase of pathologic complete response rate from the 13% in the control treatment arm to 30% pCR in the Endo-HDR arm. After randomization, we expect <5% drop-out rate.

One interim analysis for early assessment of futility is planned after 69 patients (half of the total planned sample size) have had their pCR evaluation. The trial will be terminated early if the ratio of the pCR rate in the Endo-HDR arm vs. control arm is 1 or less, i.e., the Endo-HDR treatment appears the same or worse than the control treatment by any amount. This leads to minimal loss of power compared to an analysis without intermediate look.

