14.4 Analysis of Primary Endpoint

The primary endpoint is pathologic complete response rate, which will be estimated for both arms as the proportion of patients who achieve pathologic complete response after the treatment. The corresponding 95% confidence intervals will be calculated. The comparison of pCR between the two arms will be performed using Chi-square test. The primary analysis of the pCR endpoint will be based on the intent-to-treat population which includes all randomized patients where patients are classified according to the randomized treatment assignment regardless of what treatment was received.

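### The primary pCR test uses neither the site strata from randomisation nor the baseline stage known at eligibility: a valid analysis, but with a small avoidable loss of precision and no pre-specified adjusted estimate

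*Combined protocol and SAP*

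**What the plan says.** Section 6.5 sets a 2:1 allocation (Endo-HDR to control), made "using the method of randomly permuted blocks in strata defined by study site". No other factor is named and no block size is given.

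Section 5.1 (5.1.2) admits "T2N1-2 or T3N0-2b tumors", so T and N stage must be known before a patient can be registered.

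Section 14.2.1 plans "92 in the Endo-HDR arm and 46 in the control arm" and bases power on a one-sided Fisher's exact test at 0.10.

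Section 14.4 has pCR "estimated for both arms as the proportion of patients who achieve pathologic complete response after the treatment". For the test itself, the section states: "The comparison of pCR between the two arms will be performed using Chi-square test". The analysis set is the "intent-to-treat population which includes all randomized patients". It names no stratum, covariate or sensitivity analysis for site or stage. The only regression on pCR is the exploratory treatment-by-marker model for VEGF/EGFR in section 14.5, which includes neither. The futility look (sections 14.2.1 and 14.3) also compares raw rates.

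**The concern.** The design treats site as worth balancing, and the analysis then sets it aside. If sites differ in pCR, a test that ignores the strata leaves between-site variation in the error term.

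Stage is not balanced by design, so the arms can differ in stage by chance. A crude difference carries whatever imbalance occurs, multiplied by the pCR gap between stage groups. The expected number of control pCRs is only 46 x 0.13 = 6.0, so a visible imbalance would invite argument about the result. Without a pre-specified adjusted estimate, any adjustment chosen afterwards would be open to challenge.

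**Working it through.** **The plan's own figure.** Enumerating both binomials (46 at 0.13, 92 at 0.30) with a one-sided Fisher's exact test at 0.10 gives 80.2% power, against the stated 80%. The figure reproduces. The uncorrected chi-square test at one-sided 0.10 gives 85.2% by the same enumeration. That difference comes from the change of test and has nothing to do with stratification.

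**Chance imbalance in stage.** The documents give no stage mix for this trial, so let a stage group have prevalence q of 30-50% (assumed). The 38% node-positive share in the 285-patient series of section 3.1 lies in this range. That series covered tumors within 10 cm and included T4, so it is not this trial's expected mix.

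SD of the imbalance = sqrt[q(1-q)(1/46 + 1/92)]
- q = 0.30: sqrt(0.21 x 0.0326) = 8.3 points; 95% range about +/-16; chance of 10 points or more, 21%.
- q = 0.50: sqrt(0.25 x 0.0326) = 9.0 points; 95% range about +/-18; chance of 10 points or more, 25%.

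At the interim (23 vs 46) with q = 0.50: sqrt[0.25(1/23 + 1/46)] = 12.8 points.

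**Effect on the estimate.** Shift in the pCR difference = imbalance x pCR gap between stage groups. The documents do not give this gap, so a range is assumed.

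| Assumed pCR gap by stage | SD of shift, q = 0.30 | SD of shift, q = 0.50 | 95% range, q = 0.50 |
|---|---|---|---|
| 5 points | 0.4 | 0.5 | +/-0.9 |
| 10 points | 0.8 | 0.9 | +/-1.8 |
| 15 points | 1.2 | 1.4 | +/-2.7 |
| 20 points | 1.7 | 1.8 | +/-3.5 |

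For comparison, the standard error of the difference is sqrt(0.13 x 0.87/46 + 0.30 x 0.70/92) = 6.9 points, and the design effect is 30 - 13 = 17 points.

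**What stratified testing changes.** Simulation with 5,000 trials per row, six sites (section 14.2.2) of 23 patients, blocks of 6 (assumed), q = 0.50 and one-sided 0.10. Site SD is on the log-odds scale. Figures are % power.

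| Stage odds ratio | Site SD | Unadjusted | CMH by site | CMH by stage | CMH by both |
|---|---|---|---|---|---|
| 1 | 0 | 84.4 | 84.3 | 84.3 | 83.3 |
| 1 | 0.5 | 84.2 | 84.8 | 83.5 | 83.1 |
| 2 | 0 | 84.8 | 84.6 | 85.0 | 83.5 |
| 2 | 0.5 | 84.3 | 84.5 | 84.5 | 84.0 |
| 4 | 0 | 82.9 | 82.7 | 84.5 | 83.6 |
| 4 | 0.5 | 82.1 | 82.6 | 83.8 | 83.2 |

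The Monte Carlo standard error of each figure is sqrt(0.84 x 0.16/5000) = 0.5 point. Stratifying by site moves power by -0.2 to +0.6 points, and stratifying by stage by -0.7 to +1.7. Crossing both factors costs about 1 point when stage is not prognostic. Null rejection rates were 9.0-10.6% unadjusted, 9.0-10.6% by site and 8.9-10.3% by stage (Monte Carlo standard error about 0.4 point). A further run with large site effects gave the site-stratified test +2.6 points of power and moved the null rate from 8.2% to 9.1%.

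**The case against.** An unadjusted comparison of two proportions is a defensible choice for a 138-patient phase II trial, and it matches the unadjusted sample-size calculation. Chance imbalance is already part of the standard error. No section gives pCR by T or N stage, so the stage effect is an assumption, and over most of the range shown the shift is small. At stage odds ratios of 1-2 the power differences are close to simulation noise. A site-stratified test also does nothing about stage.

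All of this stands, and it sets the weight of the point. It does not remove the case for analysing by the strata used to randomise, or for naming an adjusted estimate in advance, because both use data already in hand.

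A reader might infer that the crude pCR difference is biased, or that ignoring the site strata inflates type I error. Neither follows. Under the randomisation in section 6.5 the crude difference is unbiased on average; the shifts above are conditional on the imbalance that happens to occur. In simulation the unadjusted test stayed near 10% and became conservative when site effects were large.

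**Conclusion.** The point holds as a minor improvement in precision and pre-specification. It is not a defect of validity. The plan leaves out two pieces of information it already has: the site strata and the stage at eligibility.

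The likely benefit is 0 to about 2 points of power, somewhat more only if sites differ greatly, with type I error close to nominal. If neither site nor stage is prognostic, there is little or no gain. An unlucky stage imbalance would typically move the estimate by well under a third of its standard error (1.8/6.9 = 0.26 at the top of the SD range). These sizes rest on the assumed stage prevalence, pCR gap, site effects and block size.

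**What to change.** Leave the randomisation and the sample size as they are. In section 14.4:

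1. Make the primary test a Cochran-Mantel-Haenszel test stratified by site, one-sided at 0.10 as in section 14.2.1. Section 14.4 restates neither level nor sidedness, and it names a chi-square test where section 14.2.1 names Fisher's exact test. The same edit should settle which test is primary.
2. Fix a rule for pooling small sites before analysis. Six sites imply about one control pCR each (6.0/6), section 14.2.2 allows sites to be added, and a site with only one arm, or with no pCR, contributes nothing to the test.
3. Pre-specify, as a supportive estimate, a pCR risk difference standardised over baseline T and N stage from a logistic model. About 0.13 x 46 + 0.30 x 92 = 34 pCRs are expected, so the model should have few terms.
4. Restrict stage to the value recorded at eligibility, before randomisation. Section 6.5 lets patients be randomised before the endoscopic ultrasound that section 7.2.1 uses for staging, so a later stage could be assessed after the arm is known.

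The cost is a few sentences of SAP text and no new data. The drawback is that very small sites must be pooled. The stage-standardised estimate would not change the primary test, so the primary result would still carry any stage imbalance, with the adjusted figure reported beside it.

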7. TREATMENT PLAN AND DELIVERY

7.1 Quality Assurance

Tumor volumes and radiation plans for Endo-HDR, 3D-conformal radiation, and IMRT will be reviewed. [name] and [name] will review the first 5 endorectal plans at each institution. The first 3 3D-conformal and/or IMRT plans from each institution will be reviewed by either [name], [name], or [name]. All plans (Endo-HDR and IMRT) will be centrally reviewed by [name], [name], or [name] after completion of the study.

7.2 Endorectal Brachytherapy Radiation Therapy

7.2.1 Endorectal Brachytherapy Radiation Therapy

At the initial assessment, the surgeon will be asked to determine the likelihood of sphincter preservation. Endo-HDR is an outpatient procedure.

Patients will be treated with a daily dose of 6.5 Gy over four consecutive days for a total of 26 Gy. To administer Endo-HDR, patients will be placed in the lateral decubitus position to insert the endorectal applicator and then maneuvered into the supine position. Once in place, the applicator is secured to the plate/holder and an anal BB is placed at the anal verge. Dummy wires are inserted into the applicator and the patient is scanned using CT (2 mm slices). The radio-opaque (MRI safe-optimal) markers will guide application of the endorectal probe and assist with tumor delineation during IMRT treatment. For Endo-HDR, RT dose will be prescribed to the tumor radial margins or mesorectal node, whichever is greater not to exceed 3.5 cm from the mucosal surface. Prescribed dose will include a 1 cm CTV/PTV proximal and distal expansion excluding anal sphincter distally. However, when the GTV is close to the sphincter, the CTV should not be expanded distally into the

sphincter (treat GTV only). The endorectal applicator is flexible, with nine-channels using a high dose-rate remote after-loading system. Standard radiation procedures will be followed during Endo-HDR as outlined in the protocol. QOL will be assessed throughout the treatment process (see calendar). Endoscopic endorectal ultrasound (EUS) is obtained for tumor staging and magnetic resonance imaging (MRI) of the pelvis is used for tumor measurements (length and bulk evaluation).

7.2.2 Endorectal Brachytherapy Equipment

The treatment is delivered using a recognized endorectal applicator (Oncosmart, Nucletron) consisting of a central flexible tube with 8 catheters arranged around the circumference of a central tube. Treatment planning is performed using CT simulation. A hydraulic locking clamp mounted on a Plexiglas plate is manufactured for immobilization during the CT simulation. High dose rate brachytherapy is delivered using a Nucletron microselectron HDR (iridium-192 source).

7.2.3 Endorectal Brachytherapy Simulation

The 3D treatment planning process is carried out as follows. Prior to CT simulation, an initial anterio-posterior (AP) scout view of the patient lying in supine position is done in order to visualize the endorectal radio-opaque markers. The endorectal applicator is introduced using lubrication with the patient lying in the lateral decubitus position. The patient is then repositioned in the supine position and a Plexiglas plate with the mounted hydraulic locking clamp is slid under the patient's pelvis and the Oncosmart intracavitary mold is latched onto the hydraulic locking clamp. Repeated AP and lateral scout views are then taken and examined. When necessary, adjustments are made to the cephalic orientations of the applicator relative to the radio-opaque marker locations. The tip of the applicator will be positioned at least 2 cm beyond the proximal extent of tumor. With the applicator in the optimal position, CT scanning is performed using a slice thickness and separation of 2.5 to 5 mm to scan the area, which extends from the upper third thigh to a few cm above the tip of the endorectal applicator. Following the CT, the acquired images are sent to a dedicated virtual simulation image processing workstation. Contoured tumor, catheters and endorectal markers are incorporated into digitally reconstructed radiographs (DRRs) or digitally composite radiographs (DCRs) to enhance selectively visualization and use as references for daily treatment.

